8.1.3 Modified Physical Examination

A modified physical examination, including neurological and excluding genital/rectal examinations, will be performed. The examination should include evaluation of height (at screening only [m]); body weight (kg); waist circumference (cm); appearance and skin; head and neck; eyes, ears, nose, and throat; chest and lungs; heart; abdomen; and extremities. Neurological findings will also be recorded. All physical examination findings must be documented in the patient's study chart and also recorded in the eCRF.

8.1.4 Electrocardiogram Assessments

Each ECG assessment at screening will comprise of triplicate 10-second epochs from 12-lead ECGs recorded 5 minutes apart. Subsequent ECGs will be single 10-second epochs from 12-lead ECGs. Electrocardiogram parameters to be measured include heart rate, QRS, PR, QT, QTcB, QTcF, and RR intervals.

The ECG recordings will be made on ECG machines supplied by a central ECG laboratory. Electrocardiogram data will be transferred to the central ECG laboratory on the same day as collected and interpretation will be provided to the study site within approximately 48 hours. If any 12-lead ECG recording shows an arrhythmia other than a sinus arrhythmia, sinus tachycardia, or sinus bradycardia, an additional 12-lead ECG will be recorded to confirm the original tracing. Any other clinically significant treatment-emergent cardiac conduction abnormalities will be followed until no longer deemed necessary by the investigator.

Central interpretations of ECG recordings obtained at screening will be the basis for determination that a patient is eligible for inclusion in the study. Similarly, central interpretations of ECG recordings at baseline and other visits will be included in the final study data. However, given that interpretations of recordings will not be available for up to 48 hours, investigators are to use machine generated parameters and clinical judgment to assess cardiac function for the purposes of immediate safety concerns.

8.1.5 Vital Sign Measurements

Vital signs include: respiratory rate, oral temperature, 60-second pulse readings, blood pressure, body weight and height (height only at V1, screening), waist circumference and BMI. Vital signs are always taken after conducting the ECGs, as applicable, and prior to any other assessments, including needle sticks for laboratory or pharmacokinetic samples, scheduled for the same visit. At V1, V2, V8, and V9 vital signs include 3-positional blood pressure readings (after at least 10 minutes in the supine position, after approximately 1 minute sitting, immediately upon standing, and after approximately 3 minutes standing). Pulse will be measured by counting pulse over 60 seconds. Height will be measured only at screening. Body weight will be measured at all scheduled visits through Visit 9 (Day 57). Each patient's BMI will be calculated before Day 1 to ensure that the patient meets the BMI inclusion criterion.

Vitals sign measurements should also be collected, if feasible, at the time of an AE such as vertigo, dizziness, fall, or any sign or symptom that might indicate a fall in blood pressure.

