4 STUDY DESIGN

This is a Phase 3, randomized, double-blind, placebo-controlled, multi-center study to evaluate the efficacy and safety of lumateperone monotherapy in the treatment of patients with major depressive episodes associated with Bipolar I or Bipolar II Disorder (Bipolar Depression). The study consists of the following periods: Screening Period, double-blind On-treatment Period, and Safety Follow-up Period.

Screening Period (2 Weeks)

Potential patients will be evaluated during a Screening Period lasting up to 2 weeks, to ensure sufficient washout of restricted medications. Extension to the screening period may be approved by the Sponsor or representative in extenuating circumstances related to the patient or caregiver.

After obtaining written informed consent, diagnostic interviews and physical examinations will be conducted, vital signs and ECGs will be assessed, and blood samples for laboratory assessments will be collected. Patients considered potentially eligible for participation will be required to discontinue their current antidepressant treatment and/or other psychotropic drugs.

At baseline (Visit 2), patients who continue to meet all eligibility criteria will be randomly assigned to 1 of the 2 treatment arms for a 6-week, double-blind treatment period. Patients will be randomly assigned to 1 of the following groups: 60 mg ITI-007 or matching placebo.

Double-Blind On-Treatment Period (6 Weeks)

Patients will take their first dose of study medication the evening of their baseline visit. A single dose will be taken each day in the evening, with or without food, for the duration of the 6-week On-treatment Period.

Following randomization, patients will attend the clinic on Days 8, 15, 22, 29, 36 and 43.

Safety Follow-up Period (2 Weeks)

A return to the clinic for a safety follow-up visit will occur at Week 8, approximately 2 weeks following the last dose of study medication. If possible, patients who withdraw prematurely will be seen for an early termination visit (within 1 week of early termination) and will be asked to return to the clinic for a safety follow-up visit 2 weeks following withdrawal.

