| | | ≥40 days relative to Day 1 date and after the last dose of treatment and before the start of the Safety Follow-up Period (one day after actual Day 43 visit) | Day 43 | 6 |
| Post-treatment | Safety Follow-up | > 43 days relative to Study Day 1 date for treatment completers (42 days on-treatment) and after Day 43 post-treatment assessments. | Day 57 | 8 |

^{*} Not to exceed maximum allowed days

Baseline assessments are scheduled for Visit 2 on Relative Study Day 1, prior to first treatment of study medication. Unless otherwise specified, baseline is defined as the last non-missing measurement before the first dose of study medication.

Assessments will be considered baseline if the date of the last pre-treatment measurement is before the date of the first treatment or if the measurement was done on Study Day 1 and, according to the Study Schedule of Events, was supposed to be performed on Day 1, prior to treatment (including unscheduled measurements).

For parameters planned to be collected multiple times at the same time point (3-positional

Document: ...\ITI\ITI-007\MYA11638\Biostatistics\Documentation\SAP\ITI-007-404 SAP Final V1.0 12JUN2019.docx Author: Version Number:1.0

Version Date: 12

Page 15 of 53

blood pressure), the average of the last non-missing pre-treatment measurements will be considered as baseline.

Unless otherwise specified, the following calculations will be used for change from baseline and percent change from baseline:

Change from baseline visit will be calculated as:

Value at Visit X – Baseline Value

Percent change from baseline will be calculated as:

• Value at Visit X – Baseline Value

Baseline Value × 100

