16.4. VITAL SIGNS

The following vital signs measurements will be reported for this study:

- Systolic blood pressure (mmHg)
- Diastolic blood pressure (mmHg)
- Pulse rate (bpm)
- Respiratory rate (breaths/min)
- Oral temperature (⁰C)
- Height (cm) at screening
- Weight (kg)
- BMI (kg/m²) [calculated as weight (kg) / height (m)²]

Vital signs, including systolic blood pressure, diastolic blood pressure, pulse rate, respiratory rate, oral temperature and body weight, are recorded at screening, baseline and Days 8, 15, 22, 29, 36, 43 and 57At screening, baseline and days 43 and 57 vital signs include the 3-positional blood pressure and pulse rate will be measured after 10 minutes in the supine position, 1-minute sitting, immediately after standing, and 3 minutes after standing at screening, baseline, day 43 and day 57. These 3-positional results will be averaged at each visit and used for the summary and analyses. Pulse will be measured by counting pulse over 60 seconds. Height will be measured only at screening.

BMI measurements classify a subject's weight status as underweight, normal, overweight, or obese using Table G:. Shifts from Baseline to Day 43 will be produced by treatment group for the SAF Set to show the percentage of subjects who fall into each BMI category combination.

Document: ...\ITI\ITI-007\MYA11638\Biostatistics\Documentation\SAP\ITI-007-404 SAP Final V1.0 12JUN2019.docx Author: Version Number:1.0

Page 38 of 53

Table G: **BMI Weight Status Categories**

| BMI (kg/m²) | Weight Status |
|-------------------|---------------|
| < 18.5 | Underweight |
| 18.5 ≤ BMI < 25.0 | Normal |
| 25.0 ≤ BMI < 30 | Overweight |
| 30.0 ≤ BMI | Obese |

The following summaries will be provided for vital sign data:

- Actual and change from baseline by visit
- Incidence of markedly abnormal values
- Listing of subjects meeting markedly abnormal criteria
- Shifts from baseline by visit and time point according to markedly abnormal criteria.
- BMI shift summaries

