16.4.1. VITAL SIGNS MARKEDLY ABNORMAL CRITERIA

Markedly abnormal quantitative vital signs measurements will be identified in accordance with the following predefined markedly abnormal criteria in the table below.

...\ITI\ITI-007\MYA11638\Biostatistics\Documentation\SAP\ITI-007-404 SAP Final V1.0 12JUN2019.docx Document: Author:

Page 39 of 53

Table H: Markedly Abnormal Criteria for Vital Signs

| Variable | Unit | Low | High |
|------------|------|--|---|
| SBP | mmHg | < 90 mmHg AND | > 180 mmHg AND |
| | | decrease from baseline ≥ 20 mmHg | increase from baseline ≥ 20 mmHg |
| DBP | mmHg | < 50 mmHg AND | > 105 mmHg AND |
| | | decrease from baseline | increase from baseline ≥ 15 |
| | | ≥ 15 mmHg | mmHg |
| Pulse rate | bpm | < 50 bpm AND | > 120 bpm AND |
| | | decrease from baseline ≥ 15 bpm | increase from baseline ≥ 15 bpm |
| Weight | Kg | percentage change from baseline ≤ -7.0 % | percentage change from baseline ≥ 7.0 % |

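### Blood pressure and pulse at Days 8-36 are compared with a baseline averaged over lying, sitting and standing, so within-arm changes at five of the six on-treatment visits are not like-for-like

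*Protocol*

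**What the plan says.** Protocol 8.1.5 limits positional readings to four visits: "At V1, V2, V8, and V9 vital signs include 3-positional blood pressure readings". These are screening, baseline, Day 43 and Day 57. Each set holds four readings: "after at least 10 minutes in the supine position, after approximately 1 minute sitting, immediately upon standing, and after approximately 3 minutes standing". Two of the four are standing.

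SAP 16.4 names the same four visits and adds pulse: "the 3-positional blood pressure and pulse rate will be measured after 10 minutes in the supine position, 1-minute sitting, immediately after standing", with a further standing reading at 3 minutes. Protocol 8.1.5 names blood pressure only.

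On treatment, "patients will attend the clinic on Days 8, 15, 22, 29, 36 and 43" (Protocol 4), and SAP 16.4 has vital signs recorded at each of these visits. For the positional data SAP 16.4 states: "These 3-positional results will be averaged at each visit and used for the summary and analyses". For baseline, SAP 7 says of three-position blood pressure that "the average of the last non-missing pre-treatment measurements will be considered as baseline".

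Change is the visit value minus baseline (SAP 7). It feeds the by-visit tables, the shift tables, an MMRM and an exploratory LOCF ANCOVA (SAP 16.4), the last on-treatment value (heading of SAP 16.1) and Table H (SAP 16.4.1). In Table H the low systolic flag, for example, needs a value under 90 mmHg together with "decrease from baseline ≥ 20 mmHg". The visible text defines no posture-matched baseline for Days 8-36.

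**The concern.** Blood pressure and pulse depend on posture. Subtracting a baseline that is half standing readings from a value that is not a positional average builds a posture offset into the change. The offset is present at Days 8-36 and absent at Day 43. With no drug effect at all, each arm's mean change would step between Day 36 and Day 43 because the measured quantity changes.

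Change in vital signs is a stated safety objective, and Protocol 2.3.1 lists both postural effects and tachycardia without standing among the observed side effects. A reader of the by-visit tables, shift tables or last-value summaries would therefore want to read within-arm change as change in the patient. At five of the six on-treatment visits it cannot be read that way.

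**Working it through.** The plan gives no figure on this point to reproduce. All posture offsets below are assumptions, and I weight the four readings equally.

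**1. Visits.** On-treatment visits are Days 8, 15, 22, 29, 36 and 43. Only Day 43 is positional, so five of six are not.

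**2. Offset of the average.** Set sitting to 0, supine to s and both standing readings to t. The average is A = (s + 0 + t + t)/4 = (s + 2t)/4. Its distance above a supine reading is A - s = (2t - 3s)/4.

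Pulse, assuming t = 5 to 15 and s = -5 to 0 bpm:
- Above sitting: lowest (-5 + 10)/4 = 1.25; highest (0 + 30)/4 = 7.5 bpm.
- Above supine: lowest (10 - 0)/4 = 2.5; highest (30 + 15)/4 = 11.25 bpm.

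With no true change, the apparent change at Days 8-36 is minus these amounts.

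Systolic pressure, with assumed offsets from sitting (supine / standing at once / standing 3 min, mmHg):
- +2/-4/-2: A = (2 + 0 - 4 - 2)/4 = -1.0. Apparent change is +1.0 if later readings are seated and +3.0 if supine.
- +5/-12/-6: A = (5 + 0 - 12 - 6)/4 = -3.25. Apparent change is +3.25 seated and +8.25 supine.

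**3. Day 43.** Average minus average gives A - A = 0.

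**4. Between arms, no drug effect.** The offset is the same in both arms and subtracts out. A simulation of two arms of 175 with the larger systolic offsets and seated later readings gave a within-arm change of +3.25 mmHg. The between-arm difference averaged -0.01 mmHg (SD across runs 0.73).

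**5. Between arms, effect d confined to standing.** At Day 43 the average shows 2d/4 = d/2. A seated or supine value at Days 8-36 shows 0. For d = -8 mmHg these are -4 and 0. The terms listed for the vital-sign MMRM in SAP 16.4 include no treatment-by-visit interaction, although by-visit differences are promised. As listed, the model would pool the two quantities into one treatment effect.

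**6. Table H.** Take s = -3 and t = 10, so A = (-3 + 20)/4 = 4.25 bpm, and assume an SD of change of 10 bpm.
- Fall of 15 bpm or more: Φ(-1.5) = 6.7% without the offset; Φ((-15 + 4.25)/10) = Φ(-1.075) = 14.1% with it.
- Rise of 15 bpm or more: 6.7% without; 1 - Φ(1.925) = 2.7% with.

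These are rates for the change part only. Each blood pressure and pulse flag also needs an absolute limit. A pulse under 50 from a baseline of 65 or more has already fallen by more than 15, and a systolic value under 90 from 110 or more has already fallen by more than 20. Where both the averaged and the posture-matched baseline meet such a limit, the choice of baseline cannot alter the flag. The effect on full flags is therefore smaller, and I have not calculated it.

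**7. LOCF and last on-treatment value.** Completers supply a Day 43 average. Early dropouts supply a value from a visit that Protocol 8.1.5 does not list as positional. If dropout differed between arms by an assumed 10 percentage points, the residual offset would be 4.25 × 0.10 = 0.425, about 0.4 bpm.

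**The case against.** The strongest objection is that the text for these visits cannot be seen. Protocol 7.3-7.7 and Appendix A are not visible, and Protocol 7 refers to a study reference manual for detail. A reader might infer that Days 8-36 are single readings in an unspecified posture. The documents do not support that: the visible text gives neither the number of readings nor the posture, and either may be stated elsewhere. This stands, but it does not remove the mismatch. Whatever single posture those sources name, a baseline averaged over lying, sitting and standing does not match it.

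A reader might also infer that posture biases the comparison with placebo. It does not in by-visit mean differences: the offset is common to both arms and visit is a model factor. Nor would the SAP necessarily report a spurious late onset, because the model as listed has no treatment-by-visit term through which to show one. Nor do Table H flag rates double, since the 14.1% above is not a flag rate.

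Three smaller points also stand. Positional pulse rests on SAP 16.4 alone. SAP 16.4 plans shifts by visit and time point, which may mean by position, and the table shells are not visible. Protocol 12.4.4 treats between-group comparisons of these safety data as exploratory.

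**Conclusion.** The concern holds for within-arm change, shift tables, the change part of the Table H flags, and the LOCF and last on-treatment summaries. Each mixes a non-positional value minus an average (Days 8-36) with an average minus an average (Day 43). This follows from the SAP's own averaging and baseline rules and does not depend on which posture the unseen text names.

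Its size depends on that posture and on the assumed offsets: for pulse, 1.25-7.5 bpm relative to sitting or 2.5-11.25 bpm relative to supine. Randomised mean differences by visit are unbiased when there is no drug effect. With a standing-only effect they estimate different things at different visits: half the effect at Day 43, none at seated or supine visits. Severity is minor to moderate.

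**What to change.** Confirm the posture used at Days 8-36. If the protocol's visit text or Appendix A already states it, cross-refer; otherwise add one sentence to Protocol 8.1.5. Reconcile Protocol 8.1.5 with SAP 16.4 on whether pulse is taken by position.

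In SAP 7 and 16.4, compute baseline, by-visit change, MMRM, LOCF ANCOVA, shifts and Table H flags for blood pressure and pulse from the reading in that same posture at every visit. Apply the same rule to the last on-treatment value. Summarise the other postures at baseline, Day 43 and Day 57 separately, by position. State at the same time whether the vital-sign MMRM is meant to carry a treatment-by-visit term.

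This needs no extra measurement if the Days 8-36 posture is one of those already taken at the positional visits. The cost is that averaging no longer reduces noise at those visits and, if the chosen posture is seated or supine, a standing-only effect would appear only in the positional summary. Adding a posture-matched sensitivity table beside the averaged one would be a lesser remedy, but the main tables would still mix the two quantities.

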8.1.6 Mini International Neuropsychiatric Interview

The major clinical criterion for inclusion in the study is that the patient be diagnosed with Bipolar I or Bipolar II Disorder, meeting the DSM-5 criteria. The methodology for confirming this diagnosis is the M.I.N.I. International Neuropsychiatric Interview 7.0.2 (8/8/16 version) by [name]. The M.I.N.I. is a well-validated clinical tool (Sheehan et al., 1998). It will be used in this study at screening only to confirm the diagnosis of Bipolar Depression in patients evaluated for inclusion in the study. It will be completed by the investigator or an expert site-based rater approved by the sponsor.

8.1.7 Columbia Suicide Severity Rating Scale

The C-SSRS is a questionnaire developed and validated by Kelly Posner and colleagues (2011) for the assessment of suicidal ideation and behavior. Several versions have been developed including the "baseline" and "screening" versions and a combined "baseline/screening" version of the scale which assesses suicidal ideation and behavior in a patient's lifetime and during a predefined time period. This version can assess a patient's lifetime suicidality as well as eligibility based on inclusion/exclusion criteria. A separate "Since Last Visit" version of the scale has been developed which is used to assess suicidality since the patient's last visit. This version is meant to assess patients who have completed at least 1 initial C-SSRS assessment, and should be used in every subsequent visit. The "Since Last Visit" version of the C-SSRS addresses any suicidal thoughts or behaviors the patient may have had since the last time the C-SSRS was administered.

The C-SSRS will be administered by the investigator or an expert site-based rater, as indicated in the Schedule of Events (Appendix A).

At screening, a patient will not be eligible if he or she reports suicidal ideation of type 4 or 5 on the C-SSRS within 6 months prior to screening or any suicidal behavior in the last 2 years prior to screening, as indicated by any "yes" answers on the suicidal behavior section of the C-SSRS.

8.1.8 Young Mania Rating Scale

The YMRS is an 11-item, clinician-administered mania rating scale with established reliability, validity, and sensitivity that was designed to assess the severity of manic symptoms (Young et al 1978). Four of the YMRS items are rated on a 0 to 8 scale, with the remaining 7 items rated on a 0 to 4 scale. The total score is appropriate both for assessing baseline severity of manic symptoms and for assessing treatment-emergent manic symptoms in patients with Bipolar I or Bipolar II Disorder with Depression. It will

be completed by the investigator or an expert site-based rater according to Appendix A (Schedule of Events).

8.1.9 Clinical Global Impressions of Severity

The Clinical Global Impressions Scale (CGI) has been modified specifically for use in assessing global illness severity and change in patients with Bipolar Disorder (Spearing et al 1997). The CGI-BP-S is a standardized assessment tool that a clinician can use to rate the severity of illness, change over time, and efficacy of medication, taking into account the patient's clinical condition and the severity of side effects. The CGI-BP-S is used to document the clinician's impression of the patient's current illness state; it will be used in this study at screening (as a criterion for inclusion or exclusion) and throughout the study as a measure of efficacy. Scores on the CGI-BP-S range from 1 (not ill at all) to 7 (among the most extremely ill). A CGI-BP-S assessment will be completed at screening by the investigator or another ITI-approved expert site-based rater according to Appendix A (Schedule of Events).

8.2 Efficacy Assessments and Procedures

8.2.1 MADRS

The MADRS is a 10-item checklist designed to measure the overall severity of depressive symptoms (Montgomery and Åsberg, 1979). Individual items are rated by the investigator (or another ITI-approved expert site-based rater) according to Appendix A (Schedule of Events) on a scale of 0 to 6 in which a score of 6 represents the most severe symptoms for each item assessed. The total score ranges from 0 to 60.

Remission of Depression based on the MADRS is generally defined as a patient with a MADRS total score of \leq 12 at endpoint. A "responder" on the MADRS is defined as a \geq 50% reduction from Baseline in total MADRS score at endpoint.

The total score on the MADRS at screening is a major criterion for inclusion in the study, as well as the primary outcome measure for the study.

8.2.2 Clinical Global Impression of Severity

The CGI-BP-S will be a clinical efficacy assessment by the investigator of each patient's severity of illness, as described in Section 8.1.9.

8.2.3 Q-LES-Q-SF

The Q-LES-Q-SF is a patient self-reported questionnaire that assesses how satisfied a patient is, using a 5-point rating scale from very poor to very good, with 14 items (Endicott et al., 1993). The items assessed include physical health, mood, work, household activities, social relationships, family relationships, leisure time activities, ability to function in daily life, sexual drive/interest/performance, economic status, living/housing situation, ability to get around physically without feeling dizzy or unsteady or falling, vision in terms of ability to do work or hobbies, and overall sense of well-being that are summed to provide a raw total score ranging from 14 to 70. There are an additional 2 stand-alone items (1 for medication satisfaction and the other for overall life satisfaction). The total raw score is converted to a percent score. The Q-LES-Q-SF will be administered according to Appendix A (Schedule of Events).

8.3 Patient Placebo Questionnaire and Training:

A brief placebo response questionnaire will be administered to assess the patient's perception of likelihood their symptoms will improve as well as their perception at the end of the study whether they received placebo or active investigational drug. A brief training module will be provided describing placebo response at baseline.

